3 Participants must have completed a pain diary (PAINS-pNF) with a documented chronic target PN pain score for at least 4 days out of 7 days for at least 2 weeks during the screening period. Participants must have stable chronic PN pain medication use at baseline, defined as no clinically significant changes to prescribed chronic PN pain medication within 28 days prior to study enrolment or planned at the time of study enrolment.

4 Eastern Cooperative Oncology Group performance status of 0 or 1 with no deterioration over the previous 2 weeks prior to baseline or day of first dosing. Participants who are wheelchair bound because of paralysis secondary to a PN should be considered ambulatory when they are in their wheelchair. Similarly, participants with limited mobility secondary to a need for mechanical support (such as an airway PN requiring tracheostomy or continuous positive airway pressure) will also be considered ambulatory for the purpose of the study.

5 Participants must have at least one measurable PN, defined as a PN of at least 3 cm measured in one dimension, which can be seen on at least 3 imaging slices and have a reasonably well-defined contour. Participants who have undergone surgery for resection of a PN are eligible provided the PN was incompletely resected and is measurable. The target PN will be defined as the clinically most relevant PN, which is measurable by volumetric MRI analysis.

6 Adequate organ and marrow function as follows with no blood transfusions (of red blood cells/other blood products) within 28 days prior to screening assessment and no growth factors within 7 days prior to screening assessment:

- Haemoglobin  $\geq 9.0$  g/dL.
- Absolute neutrophil count  $\geq 1.5 \times 10^9/L$ .

- Platelet count  $\geq 100 \times 10^9/\text{L}$ .
- Total bilirubin  $\leq 1.5 \times \text{ULN}$  or  $\leq 3 \times \text{ULN}$  in the presence of documented Gilbert's syndrome (unconjugated hyperbilirubinemia).
- Alanine aminotransferase and AST  $\leq 2.5 \times \text{ULN}$ .
- Calculated creatinine clearance  $\geq 60 \text{ mL/min}$  as determined by Cockcroft-Gault (using actual body weight).

Males:

$$\text{CrCL} = \frac{\text{Weight (kg)} \times (140 - \text{Age})}{72 \times \text{serum creatinine (mg/dL)}}$$

Females:

$$\text{CrCL} = \frac{\text{Weight (kg)} \times (140 - \text{Age})}{72 \times \text{serum creatinine (mg/dL)}} \times 0.85$$

7 All participants must be able to swallow whole capsules.

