#### **9.4.2.2 Key Secondary Endpoints**

##### **9.4.2.2.1 PAINS-pNF chronic target PN pain intensity**

The key secondary estimand is the difference of the means in the change from baseline in PAINS-pNF chronic target PN pain intensity score at Cycle 12 between selumetinib and placebo, amongst participants with a PAINS-pNF chronic target PN pain intensity score  $\geq 3$  at

baseline (Pain FAS) and at least one post-baseline average cycle PAINS-pNF chronic target PN pain intensity score. Intercurrent events are addressed as follows:

- Changes to participants' chronic PN pain medication will be included assuming the treatment policy strategy to the intercurrent event of changes in participant's chronic PN pain medication.
- Post randomised study intervention discontinuation PAINS-pNF scores will not be collected and will be modelled through direct likelihood techniques assuming a hypothetical strategy to the intercurrent event of randomised study intervention discontinuation prior to end of cycle 12 due to any reason.
- PAINS-pNF scores after early crossover from placebo to selumetinib in participants with documented progression on imaging (as determined by ICR per REiNS criteria) will be set to missing assuming a while-on-treatment strategy to the intercurrent event of early crossover from placebo to selumetinib.
- PAINS-pNF scores after the first 28 days of a prolonged study intervention interruption until day prior to study intervention recommencement will be set to missing assuming a while-on-treatment strategy to the intercurrent event of prolonged study intervention interruption.
- PAINS-pNF scores after a target PN resection will be included in the analysis assuming a treatment policy approach to the intercurrent event of target PN resection.

A PAINS-pNF chronic target PN pain intensity score  $\geq 3$  at baseline is used to take into account ceiling effects. Participants with a PAINS-pNF chronic target PN pain intensity score  $< 3$  at baseline have very little or no possibility of improvement.

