Following the identification of the strongest drug class in chronic PN pain medication at each cycle, the change in score at each cycle compared to baseline will be programmatically identified following the algorithm outlined in Figure 3. If changes in the strongest drug class from baseline do not follow under the categories of Figure 3. of “Increased” or “Decreased,” the category “No Change” will be assigned. For the cycles where no PN chronic medication has been recorded in the eDiary, the change will be set to “Missing”.

A secondary definition for change from baseline in PN pain medication (Increased/Decreased/No Change) is derived using the investigator analgesic requirement assessment recorded on the e-CRF, indicating whether the reason is PN pain or other pain.

Figure 3: PN Pain Medication Score Changes Algorithm

PN, plexiform neurofibroma; WHO, World Health Organisation.

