4.2.11.2 Derivations

For both spike and chronic PN pain medication, the analgesic ladder class and the strongest analgesic ladder score for each cycle will be derived following the scoring algorithm presented in Section 3.3.8. For chronic PN pain, changes from baseline (Increased/Decreased/No Change) will also be derived as outlined in Section 3.3.8.

At each cycle, a binary variable will be derived, set to 1 if a decrease in chronic PN pain medication is observed as per definition in Section 3.3.8 and 0 otherwise. A sensitivity definition of this binary endpoint is derived using the secondary definition of decrease from baseline as assessed by the investigator when the reason for the decrease in analgesic requirement is PN pain.

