4.2.11.4 Handling of Dropouts and Missing Data

For the chronic PN pain medication based on the eDiary, the strongest class of pain medications reported over the 28 days of each cycle will be based on observed scores, that is, days with missing information will be ignored in the derivation.

For purposes of the analysis of decrease in pain medication, 1) if the pain medication data provide sufficient evidence to rule out a decrease for a cycle (see Section 4.2.9.2), that cycle is considered not to have missing pain medication data; 2) if, due to missing *daily*

pain medication data as defined in Section 4.2.9.4, the cycle does not provide sufficient evidence to rule out either an increase or a decrease in pain medication for a cycle, that cycle will be considered to have missing pain medication data.

For the investigator's assessment of change in pain medication, analyses will be based on observed data.

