4.2.11.5 Primary Analysis of Pain Medication

The pain medication decrease during the randomised period will be analysed using a random-effect logistic regression model including treatment, geographical region, and cycle number as fixed effects; baseline chronic PN pain medication score as covariates; and the following interaction terms: treatment-by-cycle number and baseline chronic PN pain medication score-by-cycle number.

A random intercept will also be included to account for variability between patients. An unstructured covariance matrix will be used to allow for unequal treatment variance and to model the correlation between different treatment measurements within the same subject. If the fit of the unstructured covariance structure fails to converge, the following covariance structures will be used in order until convergence is reached: toeplitz with heterogeneity, autoregressive with heterogeneity, toeplitz, autoregressive, and compound symmetry. All main effects and the interaction terms will remain in the model regardless of significance.

The results of the analysis are presented in terms of an odds ratio (selumetinib versus placebo) together with its 95% CI and p-value at each cycle (estimated using the treatment-by-cycle interaction coefficient) and overall, over the randomised period (based on the treatment coefficient). For each treatment arm, the odds will be presented along with the number of non-missing observations used in the estimation (n), the observed number and percentage of responders, and the corresponding 95% CIs. The analysis will be performed on a subset of the FAS population with an evaluable baseline and at least one post-baseline chronic PN pain medication score available. Data collected during the randomised period (see Section 3.3.2.2) adhering to the intercurrent event strategy (refer to Section 4.2.11.3) are included.

This analysis will be repeated using the sensitivity definition outlined in Section 4.2.11.2. For the sensitivity using investigator assessment of analgesic use, the random-effect logistic regression model will include treatment, geographical region, and cycle number as fixed effects; baseline chronic PN pain medication score as covariate; and the following interaction terms: treatment-by-cycle number and baseline chronic target PN pain medication score-by-cycle number.

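### The decrease-in-pain-medication analysis does not require analgesic use at baseline, so participants who cannot decrease may count as non-responders, and the missing-data rules conflict on their cycles

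*SAP*

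**What the plan says.** - **Endpoint.** SAP 4.2.11.2 defines a binary variable per cycle, "set to 1 if a decrease in chronic PN pain medication is observed as per definition in Section 3.3.8 and 0 otherwise". No change and increase both count as 0.
- **Scale.** SAP 3.3.8, Table 2, runs from 0 (no analgesia) to 4 (strong opioids).
- **Population.** SAP 4.2.11.5 takes the part of the FAS with "an evaluable baseline and at least one post-baseline chronic PN pain medication score available". Protocol 9.4.2.3.9 likewise names evaluable FAS participants. Neither requires a baseline score of 1 or more.
- **Entry.** Protocol 5.1, criterion 3: "Participants must have stable chronic PN pain medication use at baseline". This asks for stability, not use.
- **Model.** A random-effect logistic regression with treatment, region and cycle, "baseline chronic PN pain medication score as covariates", treatment-by-cycle and baseline-by-cycle interactions, and a random intercept. "The results of the analysis are presented in terms of an odds ratio (selumetinib versus placebo) together with its 95% CI and p-value", by cycle and overall, next to observed responder percentages.
- **Missing data.** SAP 3.3.8 says that for cycles where "no PN chronic medication has been recorded in the eDiary, the change will be set to" missing. SAP 4.2.11.4 says that "if the pain medication data provide sufficient evidence to rule out a decrease for a cycle", the cycle is not missing. SAP 4.2.9.4, to which 4.2.11.4 refers, treats a day as missing only if the gatekeeper question is unanswered, or is answered yes with no drug entered.
- **Repeat.** SAP 4.2.11.6 repeats the decrease analysis in the Pain FAS and tabulates ladder scores at baseline and each cycle, with a table of change from baseline.

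**The concern.** A participant on no chronic analgesic at baseline is at the bottom of the ladder and cannot be a responder in either arm, whatever the drug does. Counting such participants lowers both arms' percentages and can pull the odds ratio down. The protocol recognises a similar problem for pain intensity: section 9.4.2.2.1 limits that analysis because those with low baseline scores "have very little or no possibility of improvement". For medication decrease the limit is absolute, but no matching condition is set.

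At stake is whether the responder percentages and odds ratio can be read as the effect on reducing analgesics among people who take them. A second problem lies in the missing-data rules: whether a non-user's cycle enters as a 0 or is dropped depends on which SAP section is followed.

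**Working it through.** The plan gives no rate, odds ratio or power for this endpoint, so there is no figure to reproduce. All rates and shares below are assumed.

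**1. Observed percentages and crude odds ratio.** Let f be the share at score 0 in each arm and p the response probability among users. The observed proportion is (1 − f)p. With a placebo rate of 20% and a true OR of 3 among users, the selumetinib odds are 3 × 0.25 = 0.75, so p = 0.75/1.75 = 42.9%.

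| f | Placebo | Selumetinib | Crude OR |
|---|---|---|---|
| 0 | 20.0% | 42.9% | 3.00 |
| 0.2 | 16.0% | 34.3% | 2.74 |
| 0.4 | 12.0% | 25.7% | 2.54 |
| 0.6 | 8.0% | 17.1% | 2.38 |

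Example, f = 0.4: (0.257/0.743) ÷ (0.12/0.88) = 2.54. For f = 0.2, 0.4 and 0.6 the crude OR is 2.88, 2.77 and 2.67 at a placebo rate of 10%, and 2.59, 2.32 and 2.13 at 30%. The crude OR moves towards the risk ratio (42.9/20 = 2.14 in the table), never to 1.

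**2. Closer to the planned model.** These are large-sample limits of a 12-cycle random-intercept logistic model with baseline score as a linear covariate and a true subject-specific OR of 3. Users are spread evenly over scores 1 to 4. Region and the cycle interactions are left out.

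| Random-intercept SD; placebo log-odds at mid-ladder; slope per ladder step | f = 0.2 | f = 0.4 | f = 0.6 |
|---|---|---|---|
| 1.5; −2; 0 | 2.91 | 2.80 | 2.67 |
| 1.5; −1; 0 | 2.87 | 2.70 | 2.53 |
| 1.5; −1; +0.3 | 2.88 | 2.74 | 2.59 |
| 1.5; −1; −0.3 | 2.86 | 2.67 | 2.49 |
| 2.5; −2; 0 | 2.88 | 2.78 | 2.60 |

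The range is 2.91 to 2.49: (3 − 2.91)/3 = 3% to (3 − 2.49)/3 = 17% below 3. The fitted random-intercept SD also rises, from 1.5 to between 1.80 and 2.75 in the first four rows.

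**3. Where attenuation vanishes.** In a single-cycle logistic model with a linear score the limit is 2.60 to 3.06. It is 2.99 to 3.06 when decrease becomes likelier at higher scores, although the random-intercept row with a rising slope still shows some loss. With score as categories the single-cycle limit is 3.00 at every f: once given their own term, non-users carry no information about treatment.

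**4. The missing-data rules side by side.** Take a non-user who answers no every day. Under 4.2.9.4 no day is missing, and under 4.2.11.4 a decrease is ruled out, so the cycle enters as 0. Under 3.3.8 read literally, no medication is recorded and the change is missing. If 3.3.8 governs, f = 0.4, the placebo rate is 20% and non-users contribute only 10% of their cycles (assumed), the effective share is 0.04/0.64 = 0.0625 and the crude OR is 2.91. Now take a user who stops all chronic analgesics and answers no every day. This is the largest possible decrease, yet the literal 3.3.8 rule sets it to missing.

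**The case against.** - **The planned model adjusts for baseline score.** This stands in part. The crude figures are not what the model would report; adjustment and the random intercept absorb some of the dilution, sometimes all. The observed percentages are unadjusted and shrink regardless.
- **The Pain FAS repeat removes the low-pain group.** True, but it selects on pain score, so non-users with pain remain.
- **The 3.3.8 rule may already exclude non-users.** Read literally, yes for most of their cycles, but it then discards complete stoppers too. It may be meant only for cycles with no diary answer; if so, it should say so.
- **The FAS was the protocol's choice.** This stands. A restriction narrows the target population, which is why the full-FAS analysis can be kept alongside.
- **The decrease algorithm is in SAP Figure 3,** which was not available for this check. How it handles a baseline of 0 should be confirmed there.

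A reader might infer that the roughly 40 of 146 planned participants with pain below 3 (27%) are all at score 0. The documents do not say so: low pain may reflect effective medication, and non-users may have higher pain. A reader might also expect the model to fail. A larger random-intercept SD does not show that, and 4.2.11.5 gives a sequence of fallback covariance structures.

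**Conclusion.** The gap in the population definition is real: nothing requires baseline use, and score 0 cannot fall. If non-users' cycles enter, responder percentages are reduced by exactly (1 − f). Attenuation of the reported odds ratio is possible but conditional: about 3% to 17% below 3 for f between 0.2 and 0.6 in the scenarios shown, and none in some single-cycle specifications. These sizes rest on assumed shares, response rates and model parameters.

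The documents therefore do not support a flat statement that the plan dilutes the treatment odds ratio, or reading the crude odds ratios as the loss in the planned estimate. Nor do they suggest a spurious benefit: structural zeros in both randomised arms weaken an effect and do not create one. The conflict in the missing-data rules, on the literal reading of 3.3.8, needs resolving whichever population is used. The endpoint is secondary, has no power claim and lies outside the multiple testing procedure, so no confirmatory conclusion is affected.

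**What to change.** 1. Run the decrease analysis in FAS participants with a baseline chronic PN pain medication score of at least 1, as the main decrease analysis or at least as a pre-specified analysis beside the full-FAS one. Apply the same condition to the Pain FAS repeat.
2. Report the number at baseline score 0 by arm, and keep the full-FAS table of change from baseline as the descriptive summary.
3. Reconcile SAP 3.3.8 with 4.2.9.4 and 4.2.11.4 so that a recorded answer of no medication is score 0, and only absent or incomplete diary data are missing.

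The cost is one added condition and a clarified rule. The condition uses a baseline variable, so the randomised comparison is preserved. The analysis set is smaller and narrower than the protocol's, which should be noted in SAP section 2. Those removed carry no information on decrease. In an illustrative crude two-proportion comparison (73 per arm, f = 0.4, placebo rate 20%, OR 3), power is 64% in users only against 56% in everyone; with baseline adjustment the difference could be smaller. This is a cheap improvement.

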4.2.11.6 Additional Analyses of Pain Medication

Descriptive analyses of chronic PN pain medication will be produced for the FAS as follows:

- Strongest analgesic ladder category and score at baseline and at each post-baseline cycle,
- A shift table with medication that “increased,” “decreased,” or “No Change” as compared to baseline at each cycle,

Descriptive analyses of spike PN pain medication will be produced for the FAS as follows:

- Strongest analgesic ladder category at baseline and each post-baseline cycle.

Chronic and spike PN pain medications will be listed.

For the investigator assessment of pain medication during the randomised period, descriptive analyses of the number of patients whose medication “increased,” “decreased,” or “No Change” as compared to baseline at each cycle will be shown. The number of patients whose pain medication increased or decreased will also be shown separately by reason.

The analyses on PN pain medication, change in PN pain medication and PN pain medication decrease during the randomised period (except for spike medication) will be repeated for patients in Pain FAS.

4.2.11.7 Subgroup Analyses

The above analyses on the FAS and Pain FAS will be repeated per geographical region (Europe, China, Japan, Rest of World). For spike medication, the FAS analyses are repeated per geographical region and per baseline PAINS-pNF chronic target PN score categories.

4.2.12 PII-pNF Pain Interference Total Score

4.2.12.1 Definition

The PII-pNF assesses the extent to which PN pain interferes with daily functioning. All items ask the patient to consider the pain related to their PN in the past 7 days. Patients are asked how much their PN pain has made it hard for them to engage in physical activities (e.g., challenging physical activities and self-care), affected their physiological processes (e.g., sleep and energy) or impacted their social-emotional functioning (e.g., enjoyment of activities and mood). Items are rated on a 7-point Likert scale (from 0 = not at all to 6 = completely), and the total score is the mean of the completed items.

The PII-pNF is planned to be collected at the end of Cycles 1, 2, 4, 6, 8, 10, and 12 during the randomised period and at Cycles 16, 20, 24, 30, and every 6 cycles onwards.

The randomised period is defined in Section [3.3.2.2](#).

4.2.12.2 Derivations

The mean change from baseline in PII-pNF total score during the randomised period will be calculated using the patient's cycle PII-pNF score minus the baseline score.

4.2.12.3 Intercurrent Events

Follow the same approach as outlined for the 2nd key secondary endpoint in Section [4.2.2.2.3](#).

4.2.12.4 Handling of Dropouts and Missing Data

Similar to the 2nd key secondary endpoint, missing PII-pNF total scores after treatment discontinuation are handled by the “while on-treatment” approach.

4.2.12.5 Primary Analysis of PII-pNF Pain Interference Total Score

The primary analysis for PII-pNF pain interference total score will be similar to the primary analysis of the 2nd key secondary endpoint as described in Section [4.2.2.2.5](#), that is, the patient PII-pNF pain interference total score change from baseline at each cycle during the randomised period will be compared between study intervention arms using an MMRM with treatment, geographical region, average baseline chronic target PN pain intensity group and cycle number as factors as well as baseline PII-pNF pain interference total score as a covariate.

Adjusted mean change from baseline estimates per treatment group over the randomised period of study treatment and at each cycle up to Cycle 12 are presented along with 95% CIs. The corresponding treatment differences, 95% CIs, and p-values are also presented.

The analysis will be performed on a subset of the FAS population with an evaluable baseline assessment and at least one evaluable post-baseline assessment. An evaluable assessment is defined as a PII-pNF pain interference total score. Data collected during the randomised period (see Section [3.3.2.2](#)) adhering to the intercurrent event strategy (refer to Section [4.2.12.3](#)) are included.

4.2.12.6 Additional Analyses of PII-pNF Pain Interference Total Score

PII-pNF pain interference total actual scores as well as the changes from baseline at each cycle will be summarised descriptively by study intervention arm. If there are instances of early crossover, then some cycles prior to Cycle 12 will summarise data of placebo subjects who have already crossed over to selumetinib. Summary statistics will include n, mean,

standard deviation, min, Q1, median, Q3, and max. Graphical plots of the mean scores as well as change from baseline and associated 95% CIs by cycle will be produced for the randomised period.

Analysis will be performed on the FAS and the Pain FAS.

4.2.13 Patient-Reported Outcomes Measurement Information System Physical Function Items

4.2.13.1 Definition

The Adult Patient-Reported Outcomes Measurement Information System (PROMIS) Physical Function items measure self-reported capability rather than the actual performance of physical activities. Items assess upper extremity function (dexterity), lower extremity function (walking or mobility), and central regions (neck and back) as well as activities of daily living such as running errands. Patients will be assessed using the following items from the PROMIS item bank that map to physical function concepts relevant to patients with symptomatic PN:

- Does your health now limit you in bending, kneeling, or stooping?
- How much difficulty do you have doing your daily physical activities, because of your health?
- To what extent are you able to carry out your everyday physical activities such as walking, climbing stairs, carrying groceries, or moving a chair?

Items are rated on a 5-point Likert rating scale. The 7-day recall Patient-Reported Outcomes Measurement Information System Physical Function Short Form v2.0 – Physical Function 8c (PROMIS PF8c) instrument is used.

The adult PROMIS Physical Function items are planned to be collected at Baseline and at Cycles 2, 4, 8, and 12 during the randomised period as well as at Cycles 16, 20, 24, 30, and every 6 cycles onwards as per the Schedule of Activities (see Section 1.3 of the CSP).

The randomised period is defined in Section [3.3.2.2](#).

